2.3 Risk/Benefit Assessment

2.3.1 Known Potential Risks

Since this is a retrospective study and the participants will have already used the Mosie Kit, there is no potential additional physical risk from participating in the study. In some cases, because fertility is a sensitive issue, some people might become a bit emotional in recalling unsuccessful attempts to get pregnant. Otherwise, there are no known additional risks for participating in this study.

This retrospective study will be conducted as an anonymous one-time self-report survey that will contain no personal information that will allow the participant to be identified. This is done to

reduce the risk of the information being associated with the individual providing the information. This also ensures there are no immediate or long-term risks associated with participation.

2.3.2 Known Potential Benefits

The potential benefit of this study is mostly for people seeking to perform at-home intracervical insemination in the future using the Mosie Kit. Each Mosie Kit provides syringes for two inseminations to occur within a cycle at the cost of about \$89. This is less than 20% of the cost of IUI which can range between \$500-1500/ procedure before labs, ultrasounds, and additional expenses, and around 5% once all costs are added up. The study will provide valuable information to people trying to conceive about the efficiency of using the Mosie Kit for ICI, how that efficiency might compare to the effectiveness of IUI, and how the cost of each compares. This will help the user decide whether the Mosie Kit is the right conception tool for them. The study will also provide valuable information about the safety and usability of the kit. The research will let Mosie know if they have successfully communicated how to use the kit, if the instructions are clear or if any changes are needed, and whether anything else should be considered in future design changes. The study might also provide information on the timing of the insemination that might lead to a positive pregnancy outcome. Additionally, this knowledge might provide Mosie Baby with information to help it position itself better in the market..

The participant themselves will only benefit by having been able to share their experience about the Mosie Kit. While they might receive a discount code towards the purchase of a future Mosie Kit, this is not considered a benefit but a thank you for participation. Note the discount code will be a standard code used for other marketing purposes in order to ensure there is no way for Mosie staff to know if the participant obtained it for completing the survey or obtained it via other marketing avenues. The participant may feel good because they shared their experience and provided input into the Mosie Kit which will in turn help others.

The information obtained through this study will allow Mosie Baby to enhance or clarify the instructions provided with the Mosie Kit and will be considered in future production of the Mosie Kit.

2.3.3 Assessment of Potential Risks and Benefits

As stated previously there is minimal risk to the subject because this a retrospective observational study of the subject's previously chosen voluntary behavior to purchase and use the Mosie Kit. There are also minimal to no benefits to the participants for completing the survey except for their personal satisfaction of having shared and contributed to the research via their experience(s). The benefit will mainly be for people who will use the Mosie Kit in the future and who will benefit by being able to try the Mosie Kit before they resort to more expensive and invasive methods of getting pregnant. It is believed that the good of many and future possibility of having an acceptable method of artificial insemination at home outweighs the risk of participation in the study.

3 OBJECTIVES AND ENDPOINTS

OBJECTIVES	ENDPOINTS	JUSTIFICATION FOR ENDPOINTS	PUTATIVE MECHANISMS OF ACTION
Primary			
The primary objective is to understand the outcome of using the at-home intracervical insemination Mosie kit, i.e. pregnancy rate after its use.	The primary endpoints is: Pregnancy Rate after up to 6 cycles. Another primary end point is to understand the rates of pregnancy in people who desire to get pregnant without intercourse (i.e. both single and those in LGBTQ relationships.	The ultimate objective of using the Mosie Kit is to end up pregnant. Thus pregnancy rate is a primary endpoint. Specifically, pregnancy rate in up to 6 (six) cycles will be examined as it is the typical standard timeframe for attempting to get pregnant using IVI or IUI before seeking an alternative method. People who have no known fertility issue who are trying to conceive without intercourse such as those who are in LGBTQ relationships or those who are not in any relationship at all will likely have higher pregnancy rates than those with known fertility issues of female origin. Women in LGBTQ relationships wishing to conceive might also have a higher pregnancy rate than those in heterosexual relationships where infertility might be caused by things like low sperm count, sperm motility issues or erectile dysfunction (ED).	The Mosie Kit is intended to be used to deposit semen at or near the cervix where the sperm will have an increased likelihood of entering the uterus and pairing up with the ovum resulting in a pregnancy. Pregnancy rates increase when sperm reaches the ovum and fertilizes it. In people with no known fertility issues, the Mosie kit deposits the semen where it is able to fertilize the ovum. People without infertility issues who want to get pregnant without sex by using the Mosie Baby are also more likely than people with known fertility issues to get pregnant.

Secondary			
The secondary objective(s) are to understand the user's experience with the Mosie Kit and it's safety.	Secondary endpoints are: perceived ease of use and perceived safety.	The perceived ease of use is being examined as a secondary endpoint because being able to follow the instructions and use the kit as designed will directly affect whether the semen is deposited at or near the cervix having a direct effect on the results. Perceived ease of use is viewed as a mediating variable. Finally, perceived safety of the Mosie Kit will be examined. It is expected to be a moderating variable.	In order for the delivery of sperm at or near the cervix, the user needs to maximize the sperm drawn up into the Mosie syringe, insert it into the vagina, and deposit the sperm at or near the cervix. Because the Mosie syringe is inserted into the vagina, it is important to understand any perceived issues or concerns related to safety and use of the syringe.
Tertiary/Exploratory			
The tertiary objective will be to examine the pregnancy rate of people with different self-reported sources of infertility. Given the Pandemic, exploratory effect of COVID-19 on family planning, stress and pregnancy results will be examined.	Because the reason for a person's or couple's infertility might affect pregnancy rates, the reason for the infertility will also be examined. This will provide information as to whether the Mosie Kit is more effective given a specific source of infertility. The pandemic has caused an overall increase in stress, higher stress can affect fertility.	The source of infertility may play a mediating role in a successful pregnancy. For example, it might be more likely that a couple with a woman with no known infertility issue using Mosie might be more likely to get pregnant than a woman with a specific known infertility issue. Stress can play a mediating role in pregnancy. Concern over future stability and	Women who do not have a fertility issue might be more likely to get pregnant when the sperm is successfully deposited at or near the cervix. For example, this would help if the infertility was rooted in Erectile Dysfunction (ED). Stress hormones can affect pregnancy outcome. Stressful and uncertain times make people more

Page 14

planning may be family planning. expanding their families.
--

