9.4 Statistical Analyses

9.4.1 General Approach

Statistical analysis will commence with descriptive statistics for each survey question and plotting of the individual data into scatter plots to understand the data distribution. If any information suggests corrective procedures should be employed, the appropriate transformation or non-parametric test will be used.

Categorical values will be reported using descriptive statistics and frequency of occurrence. Key categorical values will also be converted into a percentage of total responses in order to allow an understanding of the prevalence of the response in the sample. For continuous variables, the means with standard deviations, median and range will be reported.

Qualitative data is only expected as a response to two questions, an open ended safety question and an additional comments question. The responses will be evaluated and categorized. Then the frequency of each category will be provided.

For inferential tests such as t-tests and ANOVAs, a p-value of 0.05 and a confidence interval of 95% will be used for statistical significance. The type of hypothesis will determine whether the specific tests will be one-tailed or two-tailed. Hypothesis seeking to understand whether there is or is not a difference will use a two-tailed test while those seeking a greater than or less than relationship will use a one-tailed test. Correlations among some of the variables will also be examined as appropriate.

Statistical analysis process for each hypothesis has already been described in section 9.1. No baseline analysis is used for cross-sectional studies. No interim analyses are planned for cross-sectional one survey studies.

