[figure not shown]
How did you or your partner time your ovulation? (Select all that apply.) *
Count days in cycle
Track vaginal or cervical fluids
Tracking changes in the cervix
Use ovulation predictor kit
Use an app to estimate ovulation
Basal Body Temperature
Wearable device
Did not time ovulation
Did using Mosie result in a pregnancy? *
O Yes
O No
Back Next Page 10 of 20

[figure not shown]
Never submit passwords through Google Forms.

 $This \ content \ is \ neither \ created \ nor \ endorsed \ by \ Google. \ \underline{Report \ Abuse} - \underline{Terms \ of \ Service} - \underline{Privacy \ Policy}$

Google Forms

Page 56

[figure not shown]

Safe process

Enjoyable

	Very Easy	Easy	Neutral	Difficult	Very Difficult
To collect the semen/sperm sample in the cup?	0	0	0	0	0
To draw up the semen/sperm in the syringe?	0	0	0	0	0
Insert the Mosie syringe into the vagina up to the handles?	0	0	0	0	0
To deposit the semen/sperm at or near the cervix using the syringe?	0	0	0	0	0
My overall impression on the ease of use	0	0	0	0	0
					Page 12 of 20
submit passwords to	through Google Fo				

MOSIE-001 © 2020 Mosie Baby Page 59

MOSIE-001 © 2020 Mosie Baby

Page 60

Pulled the syringe plunger back and forth to confirm it was functioning.

My partner washed their hands

Use a sperm friendly-lubricant.

Thawed out donor sperm from sperm bank

Prepared all items and have them handy ready to use.

Washed the penis

that	apply)?*
	Lie down in a comfortable position.
	Relax
	Receive oral sex
	Stimulate clitoris
	Use any vibratory or non-vibratory stimulation device intravaginally
	Have an orgasm
	Other:
	erall, how well were you able to use the Mosie syringe to inseminate yourself our partner? * Very Able
	our partner? *
or y O O O	our partner? * Very Able Able Not Very Able
or y 0 0 0 0	Very Able Able Not Very Able Not Able at All Volume at All Volume at All Volume at All Volume at All Able at All Volume at All Able at All Able at All
or y O O O	Very Able Able Not Very Able Not Able at All Volong did you remain laying down after using the Mosie syringe? * Less than 15 minutes

Willelf best descri	ibes your lying position? *	
On my stomach	n	
On my side		
On my back		
On my back wit	th my hips elevated by a pillow	
Other:		
O No		
O		
What type of sam	ple did you use? *	
What type of sam	ople did you use? * rom a sperm bank (frozen)	
What type of sam	rom a sperm bank (frozen)	

0 2000	thank 50%	
O 51%-	70%	
O 71% -	80%	
O 81%-	90%	
O 90%-	95%	
O 96%-	100%	

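### Ease and safety are rated by users who mostly know whether they conceived, so the survey cannot support the mediator and moderator roles in section 3, and the pooled ratings may depend on who conceived

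*Combined protocol and SAP*

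**What the plan says.** Section 3 (Objectives and Endpoints, Secondary row) states: "Perceived ease of use is viewed as a mediating variable". Its reasoning is that following the instructions and using the kit as designed "will directly affect whether the semen is deposited at or near the cervix having a direct effect on the results". Of perceived safety the same row says "It is expected to be a moderating variable". The Tertiary/Exploratory row adds "Stress can play a mediating role in pregnancy".

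All data come from one anonymous survey completed once (section 4.3). Having used the kit is an inclusion criterion (section 5.1), and section 4.1 states that there is no control group.

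In Appendix A the question "Did using Mosie result in a pregnancy" stands on the page with the footer "Back Next Page 10 of 20". The ease grid, which ends with "My overall impression on the ease of use", is on page 12. The ability-to-use item follows that grid. The safety-concern item is on page 15 and the star rating on page 16. Respondents who report a pregnancy are routed to extra pregnancy questions.

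Section 9.1 analyses Secondary Hypotheses 1, 4 and 5 descriptively. Section 9.4.1 adds: "Correlations among some of the variables will also be examined as appropriate".

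**The concern.** A mediator has to come before the outcome and carry the effect of an exposure contrast. A moderator has to be a characteristic that the outcome has not altered. Neither condition can be shown here. There is no group without the kit, and the ratings are given after the result is generally known. A user who conceived may remember the process as easier and safer, and one who did not may remember it as harder.

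Two things are at stake. First, the ease and safety percentages reported for Secondary Hypotheses 1, 4 and 5 could move with the share of responders who conceived, with the kit unchanged. Second, if ease and pregnancy turn out to be associated, section 3 supplies a ready causal reading that the data cannot support. Sections 2.3.2 and 10.1.3 say the results will inform the instructions and future production and may be used in marketing, so the reading matters in practice.

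**Working it through.** **Timing.** Section 5 restricts invitations to people who bought the kit at least 2 full months earlier and expects use within a month of purchase. Most respondents will therefore know their result before opening the form. The page order (10, then 12, 15 and 16) adds priming to that knowledge but does not create it.

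**Planned splits.** Section 4.1 divides the secondary hypotheses by age group and type of relationship. Section 9.3 stratifies by sex, age and relationship. Section 9.4.2 lists age, sex, race/ethnicity, SES, relationship preference and male/female infertility issues. None uses pregnancy status.

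**Planned models.** Section 9.1 contains no mediation or moderation test. The exploratory pregnancy model in section 9.4.3 names source of infertility, age, inseminations, cycles, lying time and relationship, with no ease, safety or stress rating. The correlations with pregnancy that section 9.1 does specify concern lying time and position. What remains open is the general correlation sentence in 9.4.1, the correlations and t-tests on how people use the kit at the end of 9.1, and the allowance for new hypotheses in 9.4.3.

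**The plan's own precision (section 9.2).** Half-width = 1.96 x sqrt(0.25/N).
- N = 500: 4.38 points (stated 4.4).
- N = 384: 5.00 points (stated 5).

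Both reproduce.

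**Illustration of the pooled shift.** The documents give no size for outcome colouring, so the following are assumptions: 50% of users who did not conceive answer 'very easy', success lifts this to 60% or 65%, and ease has no effect on conception. The overall figure is (share pregnant x lifted value) + (share not pregnant x 50%).
- Share 30%, lifted to 60%: 0.3 x 0.60 + 0.7 x 0.50 = 53.0%, a rise of 3.0 points.
- Share 30%, lifted to 65%: 0.3 x 0.65 + 0.7 x 0.50 = 54.5%, a rise of 4.5 points.
- The rise equals share x lift. Over the 10-35% range that section 4.1 quotes for IUI, it is 1.0 to 3.5 points for a 10-point lift and 1.5 to 5.3 points for a 15-point lift.
- With the 65% value, moving the share from 20% to 45% takes the overall figure from 53.0% to 56.8%. The upper share is about that of the home-insemination study in section 2.2 (13/29 = 44.8%).

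**How the same data would look as an association.** Share 30%, same assumptions:
- Lifted to 60%: pregnant among 'very easy' = 0.18/0.53 = 34.0%; among the rest = 0.12/0.47 = 25.5%.
- Lifted to 65%: 0.195/0.545 = 35.8% against 0.105/0.455 = 23.1%.

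Either table could be read as ease raising conception, although ease does nothing by construction.

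**Chance that such a comparison is significant.** If someone ran it at N = 500 (150 pregnant, 350 not), two-sided 0.05:
- 60% v 50%: SE = sqrt(0.24/150 + 0.25/350) = 0.048; z = 0.10/0.048 = 2.08; power about 55%.
- 65% v 50%: SE = sqrt(0.2275/150 + 0.25/350) = 0.047; z = 3.18; power about 89%.

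The plan does not specify this test.

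**The case against.** The strongest reply is that the disputed analysis is not in the plan. A reader might infer from section 3 that a mediation analysis is intended and invalid. Section 9 does not support that: the secondary hypotheses are descriptive and the ratings are absent from the listed model. The 55% and 89% figures are therefore not error rates of any planned test. This stands, and it limits the point to reporting and interpretation.

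The word may also be loose. Section 3 uses the same term for the source of infertility, and section 4.2 does much the same. A pre-existing diagnosis cannot mediate kit use, so the word may mean only influence. That is fair on vocabulary, but for ease section 3 spells out a causal chain from use, through deposit, to results, so the causal reading does not hang on one term.

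A reader might also infer that the question order causes the problem and that reordering would cure it. It would not. Users mostly know the outcome beforehand, and an earlier grid on the form already asks how many pregnancies they have had. Nothing in the documents sizes the priming part.

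Nor are the endpoints invalid: section 4.1 defines them as what participants perceive and report, and a perception may legitimately include the outcome. The missing piece is a view of how far it does.

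Finally, section 1.3 lists COVID-19 stress as surveyed, but no such rating is visible in the readable form. Its position relative to the pregnancy question cannot be judged.

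**Conclusion.** The point holds as one of interpretation and reporting. A single retrospective survey of kit users, rated after the outcome is mostly known, cannot distinguish ease affecting conception from success colouring the ratings, and the same limit applies to safety as a moderator. The pooled figures for Secondary Hypotheses 1, 4 and 5 may depend on the share who conceived, and no planned split would reveal it.

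On the assumed 10-15 point lift and 30% pregnant, the pooled shift of 3.0 to 4.5 points is about the size of the stated +/-4.4. The lift is an assumption, and the true colouring could be smaller or nil. Secondary Hypotheses 1 and 4 set no numerical threshold. Hypothesis 5 asks only for a majority, so a shift of this size would change its conclusion only if the result lay near one half. A genuine link between correct use and conception remains plausible, but this survey cannot isolate it.

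**What to change.** 1. Report Secondary Hypotheses 1, 4 and 5 separately for respondents who did and did not conceive, beside the total. With 150 and 350 respondents the worst-case half-widths are 1.96 x sqrt(0.25/150) = 8.0 points and 1.96 x sqrt(0.25/350) = 5.2 points, enough to show a large dependence but not a small one.
2. Place the ease, ability-to-use and safety pages before the pregnancy question and its branch. This reduces priming but does not remove knowledge of the outcome. Section 7.2 discards incomplete surveys in any case, so the move loses no outcomes that would otherwise be kept.
3. In section 3, replace the mediator and moderator wording for ease and safety with a statement that any association with pregnancy is descriptive and non-causal because the ratings were given after the outcome. Apply the same caveat to any stress rating collected in the survey.

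The cost is a page reorder, one table column and a wording change, with the IRB review that the Statement of Compliance requires for amendments. No participants or questions are added, and Appendix A already allows the form to be revised. Step 1 matters most. Step 3 alone would change little.

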4 STUDY DESIGN

4.1 Overall Design

This is a post-market retrospective cross-sectional observational study of people using the Mosie Kit for at-home insemination. The goal of the study is to understand the pregnancy rate resulting from using the Mosie Kit of people with known fertility issues or those wishing to conceive without intercourse due to medical reasons such as vaginismus or being in a LGBTQ relationship desiring a child.

This study uses a convenience sample of people who purchased the Mosie Kit in the past 8 complete months prior to the commencement of the study. The complete known list of people will be invited to participate in the study. For the primary hypothesis 1, all study participants will be treated as one group initially. Subsequently, the study participants may be divided into groups according to their age, the type of relationships (heterosexual or LGBTQ), and/or source of infertility to examine the hypothesis as it relates to these subgroups if sufficient sample size indicates this is appropriate; this analysis corresponds to the tertiary hypothesis.

Primary hypothesis 1: Pregnancy rates using the at-home insemination Mosie Kit to deposit semen near or at the cervix (i.e. intracervical insemination) are equivalent or better than traditional in doctor's office intrauterine insemination.

Given the participants can either be people with fertility issues or people in LGBTQ relationships without known problems conceiving or single women wishing to conceive, another primary hypothesis that will be examined is the difference of pregnancy rates in each of these groups. Specifically, the primary hypothesis related to this is as follows:

Primary Hypothesis 2: Pregnancy rates of LGBTQ people or single women using the Mosie Kit where the female has no know fertility issues will be higher than that of heterosexual people with a known fertility cause or those that are designated as having an unexplained fertility issue.

The secondary hypothesis will examine the use of the Mose Kit and its safety as perceived and reported by the study participants. For these hypotheses the participants will be examined as one group as well as categorized by age group and type of relationship. Specifically, the secondary hypothesis will be as follows:

Secondary Hypothesis 1: The participants perceived the Mosie Kit to be easy to use for its intended purpose.

Secondary Hypothesis 2: The participants were able to use the Mosie Kit as instructed using the instructions contained in the kit.

Secondary Hypothesis 3: The participants reported they used the kit as intended, specifically, using it within 24 hours of initial signs of ovulation and again 24-48 hours after ovulation was confirmed or expected.

Secondary Hypothesis 4: Participants reported they perceived the Mosie Kit to be a safe way to conceive.

Secondary Hypothesis 5: The majority of participants indicate they have little to no safety concerns related to using the Mosie Kit.

The tertiary hypothesis for this study dives further into the primary hypothesis by breaking out the participants into groups based on their type of relationship and the source of their infertility to examine their cohort specific pregnancy rates.

Tertiary Hypothesis 1: There will be higher pregnancy rates when using the Mosie Kit when the source of infertility is male-based than when infertility is female-based.

Tertiary Hypothesis 2: There is a difference in pregnancy rates of people or couples with known fertility issues depending on the source of their infertility. Specifically, the following sources of infertility will be examined if sufficient data is available.

- o PCOS
- Endometriosis
- Low AMH or low ovarian reserve
- Low sperm count
- Sperm motility issues
- Unexplained infertility
- Erectile dysfunction
- Performance issues or sexual anxiety, or inability to orgasm with partner.
- Vaginismus or vulvodynia
- Tilted uterus
- Multiple uterus/cervix
- Loss of a fallopian tube

Tertiary Hypothesis 3: There will be a difference between individuals who perform 2 insemination instances as described in the instructions and those that follow a different schedule or dosage number.

Additionally since we are in the midst of a pandemic with COVID-19, exploratory analysis will be conducted on the stress levels and its impact on family expansion plans.

Tertiary Hypothesis 4: COVID-19 has affected people's family expansion plans.

Tertiary Hypothesis 5: There will be a decrease in pregnancy rates in those using the Mosie Kit during the Months of March - June.

This study does not use randomization. While no control group will be examined for the study, determining the result of some of the hypotheses is based on using the reported pregnancy rate of IUI in the literature. Specifically, the reported rate of pregnancy with IUI is as high as 20% in one cycle according to the American Pregnancy Association. According to the CDC, it can range between 10-35% across 6 cycles.

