The primary objective is to understand how many people end up pregnant by using the at-home insemination Mosie

Kit during up to 6 cycles of voluntary use and how many people get pregnant using the Mosie Kit without using sex because they are either single, in a same-sex relationship, or in an unconsumated mariage due to infertility problems. The secondary objectives are to understand perceived safety and ease of use of the at-home Mosie Kit.The

tertiary objective will be to examine pregnancy outcome in relationship to self-reported reason for infertility. Additionally, since COVID-19 has recently affected

everyone, its effect on family expansion plans and stress

will also be examined.

Endpoints*: The specific study endpoints include pregnancy rates after

up to 6 cycles of at-home intracervical insemination (ICI),

perceived ease of use, perceived safety, and the

relationship of infertility source with pregnancy outcome rates, stress related to COVID-19 and its impact on family

expansion plans.

Study Population: The sample will be drawn from all people who have

purchased an at-home Mosie Kit in the past 2-8 full months

prior to the study commencement. The approximate

sample size will be 500 but all will be invited to participate.

Objectives:

MOSIE-001

Both females and males will be included in the study. It is expected that the age range of the participants will vary from approximately 21 - 50 years of age. The participants will have a history of fertility problems, specifically problems getting pregnant. Otherwise, the participants should be in overall good health. No other health conditions are being used as exclusion criteria for participation in the study. Participants may be located anywhere in the world as this study will be conducted using an online web-based survey.

Phase or Stage:

This is a post-market retrospective study to examine the experience people have with using the Mosie Kit for at-home insemination.

Description of Sites/Facilities Enrolling Participants:

No sites or facilities will be used in this study. Participants will be existing Mosie Baby Clients who have purchased a Mosie Kit in the prior 8 months. Participants may reside anywhere in the world.

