5.1 Inclusion Criteria

In order to be included in the study, the following inclusion criteria will be used.

Inclusion Criteria:

- Provide implicit consent by filling out and submitting the survey.
- Used a Mosie Kit to conceive during at least one cycle.
- At least 18 years old.
- Has an active email on file (presumed or they would not have received an invitation to participate. This information will not be verified as there is a desire to keep the survey completely anonymous.)

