9.1 Statistical Hypotheses and General Statistical Approach

The primary objective is to understand the outcome of using the Mosie kit for Intracervical insemination, i.e. pregnancy rate after its use. Specifically the hypothesis is as follows.

Primary hypothesis 1: Pregnancy rates using the at-home insemination Mosie Kit to deposit semen near or at the cervix (i.e. intracervical insemination) are equivalent or better than traditional in doctor's office intrauterine insemination (IUI). Conversely the null hypothesis is that the pregnancy rates using the at-home insemination Mosie Kit to deposit semen near or at the cervix do not have higher rates of pregnancy than in doctor's office IUI.

Analysis: Comparison of total rates of pregnancy using the Mosie Kit to the 10-20% rate reported for IUI by the American Pregnancy Association.

Primary Hypothesis 2: Pregnancy rates of LGBTQ couples or single women using the Mosie Kit where the female has no know fertility issues will be higher than that of heterosexual couples with a known fertility cause or those that are designated as having an unexplained fertility issue. The alternative hypothesis is that people with no known

fertility issues using the Mosie Kit will have less pregnancies than heterosexual couples with known fertility issues.

Analysis: Rate of pregnancy using the Mosie Kit will be obtained for the following groups: LGBTQ couples where carrying female has no known fertility issues, LGBTQ couples where carrying female has a known fertility issue, Heterosexual people with no known fertility issue, Heterosexual people with a known fertility issue, Single females with no known fertility issue and Single females with a known fertility issue. The rates of each group will be analyzed using descriptive statistics and the aggregate of the 3 groups with fertility issues will be compared with the aggregate of the 3 groups without fertility issues. An ANOVA will be used to compare the differences between groups.

Secondary Hypothesis 1: The participants perceived the Mosie Kit to be easy to use for its intended purpose. The alternative hypothesis is that the participants perceive the Mosie Kit to be difficult to use for its intended purpose.

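### Primary Hypothesis 1 judges the kit against IUI on one pooled rate, so the verdict can change with the share of respondents who have no fertility issue

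*Combined protocol and SAP*

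**What the plan says.** - **Analysis set.** Section 4.1: "For the primary hypothesis 1, all study participants will be treated as one group initially". Dividing Primary Hypothesis 1 (H1) by age, relationship or infertility source is permitted if numbers allow, and is assigned to the tertiary hypothesis.
- **Comparison.** The H1 analysis in section 9.1 is "Comparison of total rates of pregnancy using the Mosie Kit to the 10-20% rate reported for IUI by the American Pregnancy Association".
- **Benchmark.** Section 4.1 says "the reported rate of pregnancy with IUI is as high as 20% in one cycle according to the American Pregnancy Association" and, citing the CDC, "it can range between 10-35% across 6 cycles". No source population is given for either figure.
- **Who is in the sample.** The synopsis (1.1, Study Population) says "The participants will have a history of fertility problems, specifically problems getting pregnant". Section 4.1 says "the participants can either be people with fertility issues or people in LGBTQ relationships without known problems conceiving or single women wishing to conceive". The eligibility criterion on use (5.1) is "Used a Mosie Kit to conceive during at least one cycle"; neither 5.1 nor 5.2 refers to fertility status.
- **Expected difference.** Section 3 says that people without infertility issues "are also more likely than people with known fertility issues to get pregnant". Primary Hypothesis 2 (H2) and section 4.2 rest on the same expectation.
- **Planned stratification.** The H2 analysis gives rates for six relationship-by-fertility groups, then compares the three groups with issues against the three without. Section 9.4.2 has all endpoints analysed by several factors, infertility issues among them.

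**The concern.** H1 averages over a variable that the protocol itself expects to drive pregnancy rates. Who answers the email sets the weights in that average: the sample is one of convenience, and no target mix, weighting or standardisation is planned. The IUI figure has an unstated mix of its own. The pooled rate can therefore meet the benchmark because many users without fertility issues replied, or miss it because few did, with the kit performing identically in each group.

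Section 2.3.2 says the results should help users weigh the kit against IUI, and section 10.1.3 allows aggregate results in marketing. A favourable pooled verdict would be read by people with fertility issues as applying to them, although the primary analysis never tests that.

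**Working it through.** **The plan's own precision figure (section 9.2).** Half-width = 1.96 × √(0.25/n).
- n = 500: 1.96 × √(0.25/500) = 4.38%, stated as 4.4%.
- n = 384: 1.96 × √(0.25/384) = 5.00%, stated as 5%.

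Both reproduce. The fault is not in the sample size.

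**Inputs for the mix check.**
- Benchmark 35%: upper end of the 6-cycle IUI range in section 4.1.
- One-tailed test at 0.05: section 9.4.1, for directional hypotheses. H1 names no test, so this is my reading.
- 45% over 6 cycles without a fertility issue: assumed. The home-insemination arm of the cited randomised home-versus-clinic study (section 2.2) had 13/29 = 44.8% in the first 6 cycles; applying it to this stratum is an assumption.
- 25% over 6 cycles with a fertility issue: assumed. The documents give only the direction of the difference.
- Share f without a fertility issue: not stated, so varied.

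**Pooled rate.** p = 0.45f + 0.25(1 − f). It equals 35% at f = (0.35 − 0.25)/(0.45 − 0.25) = 0.50.

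**Cut-off.** At n = 500, the smallest r with P(X ≥ r | 500, 0.35) ≤ 0.05 is 194 (38.8%). At n = 384 it is 151 (39.3%).

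**Probability of passing.** Pregnancies are the sum of Binomial(nf, 0.45) and Binomial(n(1 − f), 0.25); this is the chance that the sum reaches the cut-off.

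| Share without issue | Pooled rate | Pass, n=500 | Pass, n=384 |
|---|---|---|---|
| 40% | 33% | 0.003 | 0.005 |
| 50% | 35% | 0.04 | 0.04 |
| 60% | 37% | 0.21 | 0.18 |
| 70% | 39% | 0.55 | 0.47 |
| 80% | 41% | 0.86 | 0.77 |

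The true rate with a fertility issue is 25% in every row. If the observed pooled rate is simply compared with 35% (175 or more of 500), it passes with probability 0.52 at a 50% share and 0.97 at 70%.

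**The stratum on its own.** At a 70% share, 150 of 500 respondents have a fertility issue. The same test in those 150 needs 63 pregnancies (42%), and at a true 25% it passes with probability below 0.0001.

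**Range of assumptions.**
- Fertility-issue rate 20%: crossing at (0.35 − 0.20)/(0.45 − 0.20) = 60%; pass probability 0.28 at a 70% share.
- Fertility-issue rate 30%: crossing at (0.35 − 0.30)/(0.45 − 0.30) = 33%; pass probability 0.80 at a 70% share.
- Lower benchmark of 10%, assumed rates 7% and 25%: crossing at (0.10 − 0.07)/(0.25 − 0.07) = 16.7%; cut-off 62 of 500; pass probability 0.10, 0.52 and 0.90 at shares of 20%, 30% and 40%.

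**The case against.** The strongest reply is that stratification is already planned. H2 is itself primary and yields rates with and without fertility issues. Section 9.4.2 commits to analysing all endpoints by infertility issues, and section 4.2 sets out to explore how the groups affect the overall rate. This stands as far as reporting goes. A reader might infer that a shortfall among users with fertility issues would be hidden; the documents do not support that. What remains is that H2 compares the two aggregates with each other, not with IUI, and that 9.4.2 sets no decision rule for H1.

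Four other points limit the claim:

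- The benchmark is a range, 10–20% or 10–35% over 6 cycles, with no stated decision point. A 25% rate falls short of 35% but not of 10%, so falling short depends on which end is used.
- A reader might set a cumulative kit rate against the 20% figure and call it a pass. Section 4.1 gives that figure for one cycle. At 20% per cycle the 3-cycle equivalent is 1 − 0.8³ = 48.8%, so such a comparison shows a mismatch of time basis, not an effect of mix.
- A reader might assume that the IUI benchmark describes infertile couples. The documents do not say so. Section 2.2 notes frequent use of insemination by people without a male partner and cites IUI in fertile single women.
- The mixed population is not concealed. The synopsis objectives name single and same-sex users, although the synopsis population text says otherwise.

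**Conclusion.** The point holds. The H1 conclusion rests on a pooled rate whose weights are uncontrolled, and no stratum is compared with IUI as part of it. On a single 6-cycle basis with assumed rates of 25% and 45%, the formal pooled test moves from a 0.04 to a 0.86 chance of passing as the share without fertility issues rises from 50% to 80%, with nothing else changed.

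The size rests on assumed stratum rates, the 35% benchmark and a one-sided exact test. The direction needs only that the two groups differ, as the protocol expects, and that the benchmark lies between their rates. A reader might infer that users with fertility issues will in fact do worse than IUI, or that H1 will pass wrongly. The documents give neither the mix nor the stratum rates needed to say so.

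**What to change.** 1. In section 9.1, pre-specify the H1 comparison with IUI separately for participants with and without a fertility issue, using the H2 split, each with a 95% CI. Say on which side unexplained infertility falls: the H2 hypothesis places it with known causes, but the six group labels do not.
2. Claim that the kit matches or exceeds IUI only for the stratum or strata that meet the benchmark. Keep the pooled rate as description.
3. State which benchmark value decides and its cycle basis, and compute the kit rate on the same basis. State the benchmark's source population if it is known; if not, report that as a limitation.
4. Reconcile the synopsis, section 4.1 and section 5.1 on who the study population is.

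The survey in Appendix A already asks about diagnoses and relationship type, so no new data are needed. The price is precision: with 250 per stratum the half-width is 1.96 × √(0.25/250) = 6.2%, against 4.4% for the pooled 500, and an uneven split widens the smaller stratum further.
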